2.12. Randomization Scheme and Codes

The randomization details for this study are presented in a separate randomization plan.

2.13. Handling Missing Data

Descriptive statistics and listings will be provided for all data. No substitution of missing data will be used in any calculations. Data points that appear to be spurious will be investigated and will not be excluded from the listings. Influential cases will be handled in an appropriate statistical manner.

Dates related to the adverse events and medications will be imputed using the rules below in an effort to categorize them properly into the summary tables.

Imputing partial or missing start dates:

- If the year is unknown, then the start date will not be imputed. The date will remain missing.
- If the month is unknown and the year is the same as the first dose date of the study, then impute the month and day of the date to be equal to the first dose month and day. Otherwise, impute the month as January.
- If the day is unknown and the month and year are the same as the first dose date of the study, then impute the day to be equal to the day of the first dose. Otherwise, impute the day as '01'.

Impute partial or missing stop dates:

- If the year is unknown, then the stop date will not be imputed. The date will remain missing.
- If the month is unknown, impute the month as December.
- If the day is unknown, impute the day to be the last day of the month.

If an imputed stop date is greater than the date of study completion/discontinuation date of the study, then the imputed stop date will be set equal to the date of completion/discontinuation date.

The imputed dates will be stored in the analysis datasets along with the original dates as recorded by the sites.

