| Interim Analysis | 
This study will utilize a modified adaptive design model. There will be 2 planned stages for the analysis. Stage 1 will consist of the first 30 randomized subjects. After enrollment is completed for Stage 1, enrollment will begin for Stage 2 (there will be no pause in enrollment).
 
In order to ensure an overall alpha of approximately 0.05, Stage 1 will be analyzed at an alpha level of 0.01 and the final analysis (Stage 1 and Stage 2 combined) will be analyzed at an alpha level of 0.04. A hierarchical testing strategy will be utilized in which the percentage change in PASI will be tested initially. If the p-value for this initial test is less than the indicated alpha level, the result will be concluded as real. If the percentage change in PASI is concluded as real, the change in sIGA will be tested at the indicated alpha level.
 
In order to preserve type I error, the method presented by Cui, et al will be used to combine the data from Stage 1 and Stage 2. ²²
 
The planned number of subjects for the study is 75. Stage 1 will consist of the first 30 subjects, so the weight given to Stage 1 in the analyses will be 30/75 (0.40). The weight given to Stage 2 in the analyses will be 45/75 (0.60).
 
The combining of the Stage 1 and Stage 2 analyses will be performed as follows:
 
 • The Stage 1 p-value will be converted to a Z score (standard normal score). • The Stage 2 p-value will be converted to a Z score (standard normal score). • The Z scores will be combined using the weights previously indicated to create the combined Z score. • The combined Z score will be converted to a p-value. |
| Statistical Methods | 
Analysis Sets
 
Safety population: All subjects who receive at least one dose of study drug will be included in the safety population.
 
PK/PD population: All subjects who receive the study drug and for whom at least 1 trough PK concentration was collected.
 
The safety population will be used for all summaries of subject accountability, demographic and Baseline data, and safety information, including adverse event incidence rates and laboratory
 |

data.

The PK/PD population will serve as the basis for all efficacy analyses.

Primary Efficacy Evaluation

There are two primary endpoints for this study: Percent change in PASI and sIGA response rate.

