[1] For Study Weeks 1-15: Clinic visits should occur within ± 1 days. Follow-up Visit should occur within ± 3 days.

[2] Prior and concomitant medications and supplements will be reviewed at Screening, Early Termination (ET) Visit (if applicable), and Unscheduled (UNS) Visit (if applicable). Concomitant medications and supplements will be reviewed as indicated.

[3] Physical examination will include the following organ or body system assessments: general appearance; eyes; ears, nose, and throat; head and neck; chest and lungs; cardiovascular; abdomen; musculoskeletal; lymphatic; dermatological; neurological; and extremities.

[4] Heart rate and blood pressure.

[5] Serum pregnancy test at Screening, urine pregnancy test at Visits 1, 4, 5, 6, 7, and FU Visit.

[6] See Efficacy Assessment Section under “[Cardiometabolic and Inflammatory Biomarkers](#)”.

[7] Subjects withdrawing prematurely from the trial at any visit will have the ET visit procedures completed.

[\$] Height and weight will be measured at Screening and weight will be measured at Weeks 0, 3, 7, 11, 15, and Unscheduled (UNS) Visit (if applicable).

[#] Clinical lab tests will include hematology, serum chemistry (includes a standard lipid panel), and coagulation parameters (includes an activated partial thromboplastin time (aPTT) test).

[^] AE's will only be collected after dosing on Visit 1 (Week 0).

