4 STUDY SUBJECT SELECTION AND WITHDRAWAL CRITERIA

4.1 Number of Subjects

Approximately 75 subjects will be enrolled in at least 17 sites in the US to ensure that at least 60 subjects complete the study. Subjects will be randomized in a 2:1 ratio, orticumab to placebo. Subjects who discontinue prematurely will not be replaced.

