2.2. Study Populations

Safety population: All subjects who receive at least one dose of the study drug will be included in the safety population

Intent-to-Treat (ITT) population: all subjects in whom at least one treatment was given and in whom at least one efficacy measurement was collected both at baseline and during treatment will be included in the Intent-to-Treat population.

PK/PD population: All subjects who receive the study drug and for whom at least 1 trough PK concentration is collected will be included in the PK/PD population.

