2.9.3. Psoriasis Area and Severity Index (PASI)

PASI total score, change from baseline and percent change from baseline will be calculated for each post-baseline visit. The difference between active and placebo will be tested using a mixed effects linear model (PROC MIXED in SAS) that will include fixed effects for treatment and site with Baseline PASI total score as a covariate at each post-baseline visit.

PASI75 (75% improvement from baseline in PASI total score) and PASI50 (50% improvement from baseline in PASI total score) responder rates will be derived and analyzed using a Fisher's exact test to test for differences between placebo and active at Weeks 1, 3, 7, 11 and 15.

2.9.4. static Investigator Global Assessment (sIGA)

The sIGA will be summarized at each visit using frequency counts. The difference between active and placebo will be tested using a Cochran-Mantel-Haenszel (CMH) test at each visit that sIGA is collected.

Treatment success in sIGA is defined as having a value of clear=0 or almost clear=1 and greater than or equal to a 2 point improvement on the 5-point static Investigator's Global Assessment test. Responder rates based on treatment success will be summarized and analyzed using a Fisher's Exact test at each post-baseline visit that sIGA is collected.

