5.1. Post-text Table of Contents

The following post-text tables will be generated.

Table Number	Table Title
14.1.1.1	Summary of Subject Disposition (Safety Population)
14.1.1.2	Summary of Subject Disposition (Intent-to-Treat Population)
14.1.1.3	Summary of Subject Disposition (PK/PD Population)
14.1.2.1	Summary of Demographics and Baseline Characteristics (Safety Population)

Table Number	Table Title
14.1.2.2	Summary of Demographics and Baseline Characteristics (Intent-to-Treat Population)
14.1.2.3	Summary of Demographics and Baseline Characteristics (PK/PD Population)
14.1.3	Summary of Medical History (Safety Population)
14.1.4.1	Summary of Prior Medications (Safety Population)
14.1.4.2	Summary of Concomitant Medications (Safety Population)
14.1.5.1	Summary of Study Drug Infusion (Safety Population)
14.1.5.2	Summary of Study Drug Infusion (Intent-to-Treat Population)
14.1.5.3	Summary of Study Drug Infusion (PK/PD Population)
14.2.1	Psoriasis Area and Severity Index (PASI) Parameters (Intent-to-Treat Population)
14.2.2	static Investigator Global Assessment (sIGA) (Intent-to-Treat Population)
14.2.3	Psoriasis Body Surface Area (BSA) Involvement (Intent-to-Treat Population)
14.2.4	Dermatology Life Quality Index (DLQI) (Intent-to-Treat Population)
14.2.5	Itch Numeric Rating Scale (I-NRS) (Intent-to-Treat Population)
14.2.6	Cardiometabolic and Inflammatory Biomarkers (Intent-to-Treat Population)
14.2.7	Coronary Computed Tomographic Angiography (CCTA) (Intent-to-Treat Population)
14.2.8	Trough Pharmacokinetic Concentrations (PK/PD Population)
14.3.1.1	Adverse Events Overall Summary (Safety Population)
14.3.1.2	Summary of Treatment Emergent Adverse Events by System Organ Class, and Preferred Term (Safety Population)
14.3.1.3	Summary of Treatment Emergent Adverse Events Leading to Discontinuation of Study (Safety Population)
14.3.1.4	Summary of Serious Treatment Emergent Adverse Events (Safety Population)
14.3.1.5	Summary of Treatment Emergent Adverse Events by System Organ Class, Preferred Term, and Severity (Safety Population)
14.3.1.6	Summary of Treatment Emergent Adverse Events by System Organ Class, Preferred Term, and Relationship to Study Treatment (Safety Population)
14.3.2.1	Summary of Laboratory Values - Hematology (Safety Population)
14.3.2.2	Summary of Laboratory Values – Chemistry (Safety Population)

Table Number	Table Title
14.3.2.3	Summary of Laboratory Values – Coagulation Parameters (Safety Population)

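### Subjects without a Week 15 value fall out of both primary analyses, and the efficacy set and the early-termination rule are left unsettled

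*SAP*

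**What the plan says.** **Missing outcomes.** SAP 2.13 and protocol 8.7.7 carry the same rule: "No substitution of missing data will be used in any calculations". The date-imputation rules that follow in the SAP cover adverse events and medications only.

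**PASI model.** Protocol 8.4.1 and SAP 2.9.1 call it a linear mixed model but list only treatment, site and baseline PASI. SAP 2.9.3 fits it "with Baseline PASI total score as a covariate at each post-baseline visit". No visit term, repeated effect or random effect is named.

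**Responder endpoints.** sIGA success, PASI50 and PASI75 are compared by Fisher's exact test (SAP 2.9.1 to 2.9.4). Nothing says how a missing Week 15 value is classified, and no missing-data sensitivity analysis is planned.

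**Efficacy set.** The protocol synopsis (Statistical Methods) says "The PK/PD population will serve as the basis for all efficacy analyses"; membership requires dosing and at least one trough concentration. SAP 5.1 titles its efficacy tables otherwise, for example "Psoriasis Area and Severity Index (PASI) Parameters (Intent-to-Treat Population". SAP 2.2 limits that set to dosed subjects in whom "at least one efficacy measurement was collected both at baseline and during treatment".

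**Early termination (ET).** ET shares a visit (protocol 3.2.4.1) and a column of Table 1 with Visit 7, Week 15. A footnote adds: "Subjects withdrawing prematurely from the trial at any visit will have the ET visit procedures completed".

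**Expected numbers.** Protocol 4.1: "Approximately 75 subjects will be enrolled in at least 17 sites in the US to ensure that at least 60 subjects complete the study", and "Subjects who discontinue prematurely will not be replaced".

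**The concern.** With fixed effects only and one visit per fit, the PASI analysis is an analysis of covariance on subjects measured at Week 15. PASI is collected at Weeks 1, 3, 7 and 11, but a dropout's values at those visits play no part in the Week 15 estimate. For sIGA, PASI50 and PASI75, a subject with no Week 15 value leaves the denominator.

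If leaving is related to response or tolerability, the subjects compared at Week 15 are no longer the groups as randomised. Protocol 4.4 lists adverse events and use of prohibited medication among the reasons for discontinuation, so such a link is plausible. Both primary endpoints are exposed. Three choices also remain open until data are in hand: which set is primary, whether a missing responder value is a failure, and whether an ET score is a Week 15 score.

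**Working it through.** **1. Loss allowed for.** 75 enrolled, at least 60 to complete: 75 − 60 = 15, and 15/75 = 20%. At 2:1 this is 50:25 enrolled and, if loss is proportional, 40:20 completing.

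**2. The plan's own power (SAP 2.11).** Inputs: PASI SD 10, differences 7 and 8; two-sided 0.05 is assumed because sidedness is not stated. Power = Φ(δ / (σ√(1/n₁ + 1/n₂)) − 1.96).
- 50:25: 10√(1/50 + 1/25) = 2.449. 7/2.449 = 2.858 gives 81.5%; 8/2.449 = 3.266 gives 90.4%. The stated 80% and 90% reproduce.
- 40:20: 10√(1/40 + 1/20) = 2.739. 7/2.739 = 2.556 gives 72.4%; 8/2.739 = 2.921 gives 83.2%.

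So the stated power needs all 75 subjects, whereas the analysis as written uses those with Week 15 data. sIGA behaves the same way: for 10% against 40% and 45%, exact Fisher power is 79.5% and 90.2% with 50:25, and 67.2% and 79.9% with 40:20.

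**3. sIGA illustration.** Assumed: 14/50 active and 2/25 placebo successes, 15 dropouts, all failures. This is one pooled Fisher test, ignoring the stage weighting of SAP 2.10; the final level is 0.04.

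| Lost (active+placebo) | Active | Placebo | Difference | p |
|---|---|---|---|---|
| Dropouts counted as failures | 14/50 = 28.0% | 2/25 = 8.0% | 20.0 | 0.071 |
| 10+5, completers only | 14/40 = 35.0% | 2/20 = 10.0% | 25.0 | 0.062 |
| 13+2, completers only | 14/37 = 37.8% | 2/23 = 8.7% | 29.1 | 0.016 |
| 5+10, completers only | 14/45 = 31.1% | 2/15 = 13.3% | 17.8 | 0.31 |

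The same 16 successes fall on either side of 0.04 according to who left. With equal 20% loss, both rates rise by the factor 1/0.8 and p hardly moves.

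**4. PASI illustration.** Let f be the share lost in an arm and g the completer-minus-dropout gap in mean improvement. The completer mean equals the full-arm mean plus f·g, so the bias in the difference is f_A·g_A − f_P·g_P. With g assumed to be 10 points in both arms:
- 10+5: (0.20 − 0.20) × 10 = 0
- 13+2: (0.26 − 0.08) × 10 = +1.8
- 5+10: (0.10 − 0.40) × 10 = −3.0

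These stand against a planning difference of 7.

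**5. What earlier visits could add.** If dropout is random and the last observed visit correlates ρ with Week 15, the variance ratio of a repeated-measures to a completers-only estimate is about 1 − 0.20ρ². At ρ = 0.7 this is 1 − 0.098 = 0.90. For ρ of 0.5 to 0.8 the reduction is 5% to 13%. These correlations are assumptions.

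**6. Do the two sets differ at Week 15?** Table 1 schedules six pre-dose PK draws, and PASI at Weeks 1, 3, 7 and 11. A subject who reaches Week 15 will nearly always have a trough and an on-treatment efficacy score, and so belong to both sets.

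**The case against.** Several stronger readings are tempting, and the documents do not support them.

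- **That the plan expects 20% dropout.** Protocol 4.1 gives an enrolment margin; no dropout rate is stated.
- **That the two efficacy sets would produce two primary p-values.** Step 6 shows that nearly everyone with a Week 15 score is in both. The PK/PD sentence also stands only in the synopsis; protocol 8.3 and 8.4 do not repeat it. This is a conflict to reconcile, with no demonstrated numerical effect.
- **That bias is certain or favours orticumab.** It can go either way. It is zero for the PASI difference when loss and completer-dropout gaps are equal in both arms.
- **That the distortion must be large.** Suppose the true improvements are 30% and 10%, the Week 7 to Week 15 correlation is 0.7, and everyone unimproved at Week 7 leaves. With SD 30 the completer difference is 13.5 instead of 20; with the SAP's SD of 10 it is 18.0. Both shifts are toward the null.
- **That early PASI data are thrown away.** They are analysed as secondary endpoints and are unused only for Week 15.

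A further objection is that if ET scores are mapped to Visit 7, many dropouts would be analysed after all, so the completers-only description may not hold. That is fair: the documents are silent and the table shells are in a separate file. But the silence is itself part of the gap, because a score from an early withdrawal would then stand in for Week 15.

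Finally, this is a Phase 2 proof-of-activity study with no formal sample-size assessment, and protocol 4.4 asks for reasonable efforts to obtain the ET visit. That tempers the consequences, but it does not supply the missing rules.

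**Conclusion.** The concern holds in a limited form. On the text as written, a missing Week 15 value removes a subject from both primary analyses, and nothing recovers information from that subject's earlier visits. Bias is possible, and its size and sign cannot be known in advance. Under the assumed 15 losses, the sIGA p-value runs from 0.016 to 0.31 against 0.071 with dropouts as failures, and the PASI shift from −3.0 to +1.8 points. These figures rest on assumed success counts, on all dropouts being failures, and on a 10-point PASI gap in each arm; with balanced loss the PASI shift is nil and the sIGA p-value changes little. The difference in efficacy sets and the missing ET rule are specification gaps; the first probably matters little at Week 15. All of this should be settled before any unblinded analysis, including Stage 1.

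**What to change.** 1. **One efficacy set in both documents:** all randomised and dosed subjects, analysed as randomised. Keep PK/PD for the PK summaries.
2. **PASI:** one repeated-measures PROC MIXED over Weeks 1, 3, 7, 11 and 15. Keep the site and baseline terms; add visit, treatment-by-visit and baseline-by-visit. Use unstructured covariance, with a simpler structure named in advance in case the 30-subject Stage 1 fit fails. The Week 15 treatment contrast is primary.
3. **sIGA, PASI50 and PASI75:** count a missing Week 15 value as non-response, with the observed-case analysis as sensitivity.
4. **ET scores:** assign by study day, and treat as Week 15 only inside the Visit 7 window. That window must first be reconciled: protocol 3.2.4.1 and the body of Table 1 give ±3 days, while Table 1 footnote 1 gives ±1 day for Weeks 1 to 15.

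**Cost:** SAP text, a short protocol correction and modest programming, all on data already scheduled for collection. Responder rates will fall in proportion to dropout, which may not be slight: with the 10+5 split above, the active rate is 28% rather than 35%. The repeated-measures model also relies on dropout being explained by observed data, and counting missing as failure is a stated convention, not a neutral one.

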If a subject discontinues the study prior to completion, the date the subject is withdrawn and the reason for discontinuation will be recorded in the source documents and eCRF. Although a subject will not be obliged to give his/her reason for withdrawing prematurely, the Investigator will make a reasonable effort to obtain the reason while fully respecting the subject's rights.

All subjects who are randomized and treated (i.e., received any amount of study treatment) will be included in the safety analyses. Thus, every effort will be made to contact any subject who fails to attend any Follow-up appointments/contacts, to ensure that he/she is in satisfactory health. If a subject withdraws from the study as a result of meeting discontinuation criteria (Section 4.4) after the start of study treatment administration, reasonable efforts should be made to have the subject return for the early termination evaluations (Section 3.2.4). Any subject withdrawn due to a suspected study treatment-related AE should be followed until resolution or stabilization of the event.

If a subject becomes pregnant, study treatment will be discontinued immediately. The subject will be followed until delivery or other termination of pregnancy for outcome.

The Sponsor has the right to terminate this study, and the Investigator/Investigational Site has the right to close the site, at any time, although this should occur only after consultation among involved parties. The Investigator will notify the IRB in writing of a premature termination of a study or closure of Investigational Site and will send a copy of the notification to the Sponsor.

Events that may trigger premature termination of a study or closure of an Investigational Site include, but are not limited to, a new toxicity finding, a request to discontinue the trial from a regulatory authority, non-compliance with the protocol, GCP violations, slow recruitment/low enrollment, or change in development plans for the study treatment.

Enrollment of new subjects and dosing of ongoing subjects will be temporarily stopped based on the stopping criteria (See Section 12.2). The Investigator, Sponsor, and the Medical Monitor will discuss whether a lower dose or any additional treatment guidelines should be implemented, or if the trial should be permanently stopped. Any proposed changes to the protocol to address such findings will be submitted for review and approval by the IRB and FDA prior to re-starting the trial.

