7.4 Eliciting and Reporting of Adverse Events

AE monitoring will start immediately following the first dose at Visit 1 and will continue through the Follow-up Visit. Any subject with a possible study treatment-related AE at the Follow-up Visit will be followed until resolution or stabilization of the event. Further, any SAE, whether related or unrelated to study treatment that occurs within 30 days following the last dose of study treatment will be followed until resolution or stabilization of the event. This may require additional clinical assessments and laboratory tests. The follow-up results will be recorded in the subject's source documentation and in the eCRF.

Subjects will be instructed to report all AEs experienced during the study, and subjects will be assessed in clinic for the occurrence of AEs throughout the study. To avoid bias in eliciting AEs, subjects will be asked general, non-leading questions such as "How are you feeling?"

All AEs, including pretreatment and TEAEs, reported by the subject, observed, or otherwise identified by the Investigator or other Investigational Site personnel will be documented.

Medical conditions existing at Screening should be recorded as medical history. New or worsening pre-existing medical conditions or diseases are considered AEs if they arise or worsen after dosing (Visit 1) and should be recorded as AEs.

Surgical procedures themselves are not AEs; they are therapeutic measures for conditions that require surgery. The condition for which the surgery is required is an AE if it occurs or is detected following the first dose of study treatment at Visit 1 through the Follow-up Visit. Conditions leading to planned surgical procedures are not AEs if the condition(s) was (were) known before study treatment. In the latter case, the condition should be reported as medical history.

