2.7. Safety Evaluations

2.7.1. Adverse Events

Adverse events will be coded using the Medical Dictionary for Drug Regulatory Affairs (MedDRA) version 24.0 and tabulated, including categorical information of interest such as onset and resolution times, time of onset relative to dose, severity at onset, maximum severity, causal relationship to study medication, and action taken.

Treatment-emergent adverse events (TEAEs) are defined as any AE that starts or increases in severity after the first randomized dose of study treatment. The incidence of TEAEs will be tabulated by MedDRA preferred term, system organ class, treatment group, severity, and assigned relationship to study treatment. Adverse events will also be summarized by severity and relationship to the investigational product (IP).

The incidence of serious AEs, drug-related AEs, serious and drug-related AEs, and any AEs resulting in discontinuation from the study will be listed.

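### SAP 2.13 sets no consistency limits on imputed dates, so an imputed AE stop or start can contradict a month, year or stop date that the site recorded

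*SAP*

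**What the plan says.** SAP 2.13 gives the purpose of the rules, which is to place records correctly in the tables: "Dates related to the adverse events and medications will be imputed using the rules below in an effort to categorize them properly into the summary".

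- **Start, day unknown, same month and year as first dose:** "then impute the day to be equal to the day of the first dose".
- **Start, month unknown, same year as first dose:** "then impute the month and day of the date to be equal to the first dose month and day".
- **Stop:** an unknown day becomes the last day of the month and an unknown month becomes December. If the imputed date is later than completion or discontinuation, "then the imputed stop date will be set equal to the date of completion/discontinuation date".

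The start rules do not refer to the stop date. The cap does not refer to the recorded month or year, or to the event's own start. The section also says that the analysis datasets keep the imputed dates beside the dates the site entered.

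Protocol 4.4 says: "Any subject withdrawn due to a suspected study treatment-related AE should be followed until resolution or stabilization of the event". Protocol 7.4 says: "Any subject with a possible study treatment-related AE at the Follow-up Visit will be followed until resolution or stabilization of the event". Protocol 7.4 also follows serious adverse events (SAEs) arising within 30 days of the last dose, and has follow-up results entered in the eCRF.

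SAP 2.7.1 tabulates AEs with information "such as onset and resolution times, time of onset relative to dose".

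**The concern.** An imputed date should stay inside what the site wrote down. These rules can leave it. The cap suits a record that is compatible with exit, such as a stop in the exit month with the day missing. Applied to a stop recorded in a later month, it returns a date that the record rules out. The events exposed are those that outlast participation, among them related AEs that led to withdrawal, and their resolution times would come out too short.

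The start rule has a similar gap. Assigning the first-dose date is the usual conservative choice when nothing else is known. When a known stop shows that the event ended before dosing, it places onset after resolution. That touches the split between pretreatment and treatment-emergent events, and treatment-emergent incidence is part of a primary safety endpoint (SAP 1.3.4).

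**Working it through.** The plan gives no figure to reproduce. The check applies the SAP 2.13 rules literally to test dates. All calendar dates below are assumptions. Day 120, the scheduled Follow-up Visit, is from Protocol 3.2.5.1.

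**1. Stop-date cap**

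Rule: imputed stop = last day of the recorded month; if later than exit, stop = exit.

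| Exit | Recorded stop | After month-end rule | After cap | Days before the recorded month's first and last day |
|---|---|---|---|---|
| 10 Aug | Sep, day unknown | 30 Sep | 10 Aug | 22 and 51 |
| 10 Aug | 20 Sep, complete | not imputed | 20 Sep kept | none |
| 17 Oct 2021 | Nov 2021, day unknown | 30 Nov | 17 Oct | 15 and 44 |
| 17 Oct 2021 | Oct 2021, day unknown | 31 Oct | 17 Oct | consistent with the record |
| 17 Oct 2021 | 2022 only | 31 Dec 2022 | 17 Oct 2021 | wrong year |

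The 17 Oct exit is Day 120 after a first dose on 20 Jun 2021 (20 Jun + 119 days). First row: 10 Aug to 1 Sep is 22 days, and 10 Aug to 30 Sep is 51 days. The first two rows show that the result turns on whether a day was entered.

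Taking every first-dose day in 2021 with exit at Day 120, and a day-unknown stop in the month after exit, the capped date left the recorded month in 365 of 365 cases, by 1 to 61 days.

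The cap can also precede the event's own start. Early-terminated subjects are discharged at the ET visit (Protocol 3.2.4.1), while SAE reporting runs to 30 days after the last dose (Protocol 7.4.2). Take first dose 20 Jun, last dose Day 22 (11 Jul), exit Day 30 (19 Jul), and an SAE starting 3 Aug, 23 days after the last dose. A stop recorded as Aug becomes 19 Jul, 15 days before the recorded start.

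**2. Start rule**

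Rule: a start with unknown day in the first-dose month becomes the first-dose date.

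- First dose 10 Jun, start Jun, stop 5 Jun: imputed start 10 Jun, 5 days after the stop.
- First dose 20 Jun, start Jun, stop 10 Jun: imputed start 20 Jun, 10 days after the stop. With only the year recorded, the month-unknown rule gives 20 Jun as well.

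Over all first-dose days in 2021, paired with every known stop earlier in the same month, there are 7 × 465 + 4 × 435 + 378 = 5,373 combinations (31-, 30- and 28-day months). Start is after stop in all 5,373, as it must be when the rule ignores the stop.

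**3. What the wrong dates reach**

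- *Treatment-emergent status* (SAP 2.7.1) depends on start or worsening, so the cap cannot change it.
- *Prior or concomitant status* (SAP 2.6) depends only on whether the stop precedes first treatment. A stop moved to exit is still after first treatment, and the imputed start is not used. Neither rule changes it.
- *Resolution time* uses the stop date, so the cap makes it wrong.
- *Pretreatment class* (Protocol 8.7.1) requires occurrence before Visit 1/Day 1. An onset imputed to Day 1 takes the event out of that class even though its stop shows it belongs there.

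**The case against.** The strongest reply is that little in the reported tables moves. Complete dates are not touched, site entries are kept, and SAP 4.2 lists all data. None of the AE table titles in SAP 5.1 names duration or resolution time. AE outcome is a separate eCRF field with its own unresolved category (Protocol 7.4.1 and 7.7.1), so a capped stop does not by itself report an event as recovered. Queries (Protocol 9.1.1) should remove many partial dates. All of this stands, and it limits the size of the problem. It does not make the capped date right, and SAP 2.7.1 does say that resolution times are tabulated.

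A reader might infer three stronger things:

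- *That the rules replace dates the site recorded.* They do not. Only the imputed analysis date departs from the recorded month, year or stop.
- *That false treatment-emergent events will follow.* This needs an AE that ended before dosing to be in the data. The Protocol Table 1 footnote collects AEs only after dosing at Visit 1, and Protocol 7.4 starts monitoring after the first dose. Yet 7.4 also documents pretreatment AEs, and 8.7.1 plans a listing of them. The SAP's own output lists name no pretreatment-AE output. The SAP also does not say whether a start imputed to the first-dose day counts as after the dose. The route is possible but conditional.
- *That AEs with an unknown start year drop out of the treatment-emergent tables.* SAP 2.13 says only that the date stays missing. Exclusion is not stated, and an onset with an unknown year is remote in a study this short.

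**Conclusion.** The point holds as a minor defect: a stated rule, followed literally, gives analysis dates that the record contradicts.

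- **Cap:** wrong resolution times for AEs whose partial stop is recorded in a month or year after exit, a situation the protocol's follow-up rules make foreseeable. In the worked case the error is 22 to 51 days.
- **Start rule:** onset after resolution whenever a known stop precedes first dose and the start is partial in the first-dose month or year. If pre-dose AEs are recorded, the event leaves the pretreatment class and may be counted as treatment-emergent.

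With 75 subjects at 2:1 (50 and 25), one subject wrongly counted moves incidence by 1/50 = 2 or 1/25 = 4 percentage points, but only if that subject has no other qualifying event.

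The documents do not allow an estimate of how often either case arises; it is probably seldom. The day counts above are conditional on a qualifying record and are not error rates. Efficacy is not affected.

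**What to change.** In SAP 2.13:

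1. Apply the completion/discontinuation cap only where the recorded year and month allow a date on or before exit. An imputed stop is then never earlier than the first day of a recorded month, and it should also never be earlier than the event's own start.
2. Add that an imputed start may not be later than a known stop date; if it is, use the stop date.

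Under these limits, a stop recorded as Sep with exit on 10 Aug stays at 30 Sep. A start recorded as Jun with a stop of 5 Jun becomes 5 Jun and is classed as pretreatment.

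The Protocol Table 1 footnote should also be reconciled with Protocol 7.4 and 8.7.1 on whether pre-dose AEs are recorded, because the consequence of the start rule depends on it.

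The cost of the SAP change is two lines of text and a small change to the derivation program. No new data are needed.
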